6.4 Safety

The Principal Investigator is responsible for ensuring that all staff involved in the study is familiar with the content of this section.

6.4.1 Definition of adverse events

An AE is the development of an undesirable medical condition or the deterioration of a pre-existing medical condition following or during exposure to a pharmaceutical product, whether or not considered causally related to the investigational product. An undesirable medical condition can be symptoms (e.g., nausea, chest pain), signs (e.g., tachycardia, enlarged liver) or the abnormal results of an investigation (e.g., laboratory findings, ECG). In clinical studies, an AE can include an undesirable medical condition occurring at any time, including run-in or washout periods, even if no study treatment has been administered.

The term AE is used to include both serious and non-serious AEs.

6.4.2 Definitions of serious adverse event

A SAE is an AE occurring from the time of informed consent (Visit 1) was obtained for the duration of the study, up until the last contact, Visit 9 (End of Study Visit) that fulfils one or more of the following criteria:

- Results in death
- Is immediately life-threatening
- Requires in-patient hospitalisation or prolongation of existing hospitalisation
- Results in persistent or significant disability or incapacity
- Is a congenital abnormality or birth defect
- Is an important medical event that may jeopardise the patient or may require medical intervention to prevent one of the outcomes listed above

In addition, the following events (**regardless of whether or not they meet any of the serious criteria above**) will be collected as SAEs:

- Cancer
- Drug dependency/abuse

Serious AEs related to skin lesions, infection, lymphocytopenia, thrombocytopenia and symptomatic hand and foot oedema should be given special attention.

For further guidance on the definition of a SAE, see [Appendix B](#) to the Clinical Study Protocol.

For the purposes of regulatory reporting, the following events/medical concepts should be transmitted as described in Section 6.4.4 below in the same timelines as SAEs regardless of whether the reports are classified as serious or non-serious:

- Pancreatitis
- Opportunistic infections (eg, tuberculosis, Herpes zoster, cytomegalovirus, Pneumocystis jirovecii, etc)
- Serum AST or ALT ≥ 3 x ULN and serum total bilirubin > 2 x ULN or evidence of jaundice.

6.4.3 Recording of adverse events

6.4.3.1 Time period for collection of adverse events

Adverse events will be collected from the time informed consent was obtained for the duration of the study, up until the last contact, Visit 9 (End of Study Visit).

Serious AEs will be collected from the time of signature of informed consent throughout the study until and including the last contact, Visit 9 (End of Study Visit).

6.4.3.2 Adverse event dictionary

The latest version of the Adverse Event dictionary, Medical Dictionary for Regulatory Activities (MedDRA), will be used for the classification and analysis of AEs entered in the study database. For regulatory reporting, SAEs will be processed at the Bristol-Myers Squibb Pharmacovigilance database and coded using MedDRA.

6.4.3.3 Variables

The following variables will be collected for each AE:

- AE (verbatim)
- The date when the AE started, stopped or was ongoing
- Maximum intensity (if AE changes in intensity, the severest intensity is to be documented in the eCRF, the duration of the AE reported in the eCRF should however describe the total time of occurrence of the AE).
- Whether the AE is serious or not
- Investigator causality rating against the investigational product (Yes or No)
- Action taken with regard to investigational products:
 - Not applicable: For AE occurring during the pre-treatment period as well as during the 30 days follow-up of an AE after last investigational product administration (Visit 9).
 - No change: Investigational product dosing remained the same in spite of AE being present.
 - Temporarily discontinued: Investigational product usage is temporarily discontinued because of the AE, either because the patient chooses to discontinue the investigational product or the physician feels it is in the patient's best interest to temporarily discontinue the investigational product.
 - Permanently discontinued: Investigational product usage is permanently discontinued because of the AE, either because the patient chose to discontinue

the investigational product or the physician feels it is in the patient's best interest to discontinue the investigational product.

- Other: Other countermeasures are required such as an operative procedure.
- AE caused patient's withdrawal from study (Yes or No).
- Outcome:
 - Resolved: The AE is no longer present at any intensity - symptoms have completely abated.
 - Resolving: The AE is abating, but has not completely resolved yet.
 - Not resolved: The AE has not resolved, but is still present with the same intensity.
 - Resolved with sequelae: The AE resolved but has resulted in consecutive symptom(s).
 - Worsened: The AE is still present but at a heightened intensity. The rule of repetition of AE reporting should be applied.
 - Fatal: The AE directly caused or contributed to the patient's death.
 - Unknown: There is no information available on the outcome of the AE.

In addition, the following variables will be collected for SAEs:

- Date AE met criteria for SAE
- Date investigator became aware of SAE
- Reason for classification as serious
- Date of hospitalisation
- Reason for hospitalization
- Date of discharge
- Probable cause of death
- Date of death
- Autopsy performed
- Causality assessment in relation to study procedure(s)

- Causality assessment in relation to other medication
- Description of AE

If the intensity of an AE changes only the maximum intensity of the event will be recorded. Intensity is defined as one of the following:

- Mild: Awareness of event, but easily tolerated. Symptoms can be ignored and disappear when the patient is distracted. They do not interfere with the patient's daily activities and are not clinically relevant.
- Moderate: Symptoms cause discomfort but are tolerable, they cannot be ignored and affect concentration. Symptoms may interfere with the daily activities and may be clinically relevant.
- Severe: Symptoms affect usual daily activity (inability to carry out usual activity) and are clinically relevant.
- Very Severe: Debilitating, significantly incapacitates patient despite symptomatic therapy.

It is important to distinguish between serious and severe AEs. Severity is a measure of intensity whereas seriousness is defined by the criteria in Section 6.4.2. An AE of severe intensity need not necessarily be considered serious. For example, nausea that persists for several hours may be considered severe nausea, but not a SAE. On the other hand, a stroke that results in only a limited degree of disability may be considered a mild stroke but would be a SAE.

6.4.3.4 Causality collection

The investigator will assess causal relationship between the investigational product and each AE, and answer 'Yes' or 'No' in the eCRF to the question 'Do you consider that there is a reasonable possibility that the event may have been caused by the investigational products?' If there is any valid reason, even if undetermined or untested, for suspecting a possible cause-and-effect relationship between the investigational products and the occurrence of the AE, then this answer should be 'Yes'. Otherwise, if no valid reason exists for suggesting a possible relationship, then this answer should be 'No'. If more than one AE is identified, a causality assessment should be made for each AE.

For SAEs the causal relationship will also be assessed for other medication and study procedures. Note that for SAEs that could be associated with any study procedure the causal relationship is implied as 'Yes'.

A guide to the interpretation of the causality question is found in [Appendix B](#).

6.4.3.5 Adverse Events based on signs and symptoms

All AEs spontaneously reported by the patient or reported in response to the open question from the study personnel: ‘Have you had any health problems since the previous visit?’, or revealed by observation will be collected and recorded in the eCRF. When collecting AEs the recording of diagnoses is preferred (when possible) to the recording of a list of signs and symptoms. However, if a diagnosis is known and there are other signs or symptoms that are not generally part of the diagnosis, the diagnosis and each sign or symptom will be recorded separately.

6.4.3.6 Adverse events based on examinations and tests

The results from Clinical Study Protocol mandated laboratory tests and vital signs will be summarised in the Clinical Study Report (CSR). Deterioration as compared to baseline in protocol-mandated laboratory values, vital signs and other safety variables should therefore only be reported as AEs if they fulfil any of the SAE criteria or are the reason for discontinuation of treatment with the investigational product.

If deterioration in a laboratory value/vital sign is associated with clinical signs and symptoms, the sign or symptom will be reported as an AE and the associated laboratory result/vital sign will be considered as additional information. Wherever possible, the reporting investigator uses the clinical, rather than the laboratory term (e.g., anaemia versus low haemoglobin value). In the absence of clinical signs or symptoms, clinically relevant deteriorations in non-mandated parameters should be reported as AE(s).

Deterioration of a laboratory value, which is unequivocally due to disease progression, should not be reported as an AE/SAE.

Any new or aggravated clinically relevant abnormal medical finding at a physical examination as compared with the baseline assessment will be reported as an AE.

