6. FPG > 12.2 mmol/L (>220 mg/dL) during the double-blind treatment period, between Visit 6 and Visit 9, confirmed at repeated measurement within 5 days (results from central laboratory). If self-monitored FPG > 12.2 mmol/L (>220 mg/dL) between Visit 6 and Visit 9, to repeat the self-monitoring of FPG within 2 days. If this second FPG is still >12.2 mmol/L (>220 mg/dL), the patient should contact the study centre and have this measure confirmed by central laboratory within 5 days for discontinuation.
7. Calculated CrCl <60 ml/min or an increase in serum creatinine of ≥ 44.2 μ mol/L (≥ 0.5 mg/dL) above the baseline value confirmed at a repeated measurement within 1 week.
8. Serum total bilirubin >34 μ mol/L (>2 mg/dL) confirmed at a repeated measurement within 1 week.
9. Increase of ALT and/or AST >3 x ULN and increase of total bilirubin ≥ 2 x ULN confirmed at a repeated measurement within 1 week.
10. Increase of ALT or AST >5 x ULN confirmed at a repeated measurement within 1 week.
11. A temporary discontinuation of investigational product must occur when the patient receives intravascular administration of iodinated contrast agents. Since intravascular administration of iodinated contrast agents in radiologic studies can lead to renal failure, both metformin and investigational product should be temporarily stopped prior to, or at the time of the test and not re-instituted until at least 48 hours afterwards. Investigational product and metformin should also be temporarily stopped 48 hours before elective surgery with general anaesthesia and should not be resumed earlier than 48 hours afterwards.

5.8.1 .Procedures for discontinuation of a subject from investigational product

A patient that decides to discontinue the investigational product will always be asked about the reason(s) and the presence of any AEs. If possible, they will be seen and assessed by an

investigator(s). Adverse events will be followed up (See Sections 6.4.3 and 6.4.4); diary cards, glucometers, and the investigational product should be returned by the patient.

Randomised patients who do not complete the study should complete the procedures described for Visit 9 (End of Study Visit).

If a patient is withdrawn from the study, see Section 5.9.

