6.4.3.7 Disease progression

Disease progression can be considered as a worsening of a patient’s condition attributable to the disease for which the investigational product is being studied. It may be an increase in the severity of the disease under study and/or increases in the symptoms of the disease. Events, which are unequivocally due to disease progression, should not be reported as an AE during the study.

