6.4.4 Reporting of serious adverse events

All SAEs have to be reported, whether or not considered causally related to the investigational product, or to the study procedure(s). All SAEs will be recorded in the eCRF.

If any SAE occurs in the course of the study, then investigators or other study centre personnel will inform appropriate AstraZeneca representatives within one day, i.e., immediately but **no later than the end of the next business day** of when he or she becomes aware of it.

The designated AstraZeneca representative works with the investigator to ensure that all the necessary information is provided to Bristol-Myers Squibb Global Pharmacovigilance & Epidemiology **within one calendar day** of initial receipt for all SAEs. The AstraZeneca representative will notify the appropriate Bristol-Myers Squibb Pharmacovigilance contact to ensure regulatory compliance.

For fatal or life-threatening AEs where important or relevant information is missing, active follow-up is undertaken immediately. Investigators or other study centre personnel will inform AstraZeneca representatives of any follow-up information on a previously reported SAE within one calendar day, i.e., immediately but **no later than the end of the next business day** of when he or she becomes aware of it.

The reference document for definition of expectedness is the Investigators Brochure for the investigational product and the European Union (EU) Summary of Product Characteristics (SPC) for the active comparator product.

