- Consistency with known drug profile. Was the AE consistent with the previous knowledge of the suspect drug (pharmacology and toxicology) or drugs of the same pharmacological class? OR could the AE be anticipated from its pharmacological properties?
- Dechallenge experience. Did the AE resolve or improve on stopping or reducing the dose of the suspect drug?
- No alternative cause. The AE cannot be reasonably explained by another aetiology such as the underlying disease, other drugs, other host or environmental factors.
- Rechallenge experience. Did the AE reoccur if the suspected drug was reintroduced after having been stopped? AstraZeneca would not normally recommend or support a rechallenge.
- Laboratory tests. A specific laboratory investigation (if performed) has confirmed the relationship?

A “reasonable possibility” could be considered to exist for an AE where one or more of these factors exist.

In contrast, there would not be a “reasonable possibility” of causality if none of the above criteria apply or where there is evidence of exposure and a reasonable time course but any dechallenge (if performed) is negative or ambiguous or there is another more likely cause of the AE.

In difficult cases, other factors could be considered such as:

- Is this a recognised feature of overdose of the drug?
- Is there a known mechanism?

Ambiguous cases should be considered as being a “reasonable possibility” of a causal relationship unless further evidence becomes available to refute this. Causal relationship in cases where the disease under study has deteriorated due to lack of effect should be classified as no reasonable possibility.

Clinical Study Protocol Appendix C

Drug Substance	Saxagliptin
Study Code	D1680L00006
Edition Number	1
Date	

**Appendix C
International Airline Transportation Association (IATA) 6.2 Guidance
Document**

LABELLING AND SHIPMENT OF BIOHAZARD SAMPLES

International Airline Transportation Association (IATA) classifies biohazardous agents into 3 categories (http://www.iata.org/whatwedo/cargo/dangerous_goods/infectious_substances.htm). For transport purposes the classification of infectious substances according to risk groups was removed from the Dangerous Goods Regulations (DGR) in the 46th edition (2005). Infectious substances are now classified either as Category A, Category B or Exempt. There is no direct relationship between Risk Groups and categories A and B.

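### The disease-progression exemption in Protocol 6.4.3.6 and 6.4.3.7 has no exception for events that are serious or end treatment, and so conflicts with the duty to report all SAEs

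*Protocol*

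**What the plan says.** The protocol contains two sets of reporting rules that bear on the same event.

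Rules that exempt:
- Section 6.4.3.6, third paragraph: "Deterioration of a laboratory value, which is unequivocally due to disease progression, should not be reported as an AE/SAE".
- Section 6.4.3.7: "Events, which are unequivocally due to disease progression, should not be reported as an AE during the study". On what counts as progression, the section adds: "It may be an increase in the severity of the disease under study and/or increases in the symptoms of the disease".

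Rules that require a report:
- Section 6.4.3.6, first paragraph, on deterioration in protocol-mandated laboratory values and other safety variables: these "should therefore only be reported as AEs if they fulfil any of the SAE criteria or are the reason for discontinuation of treatment".
- Section 6.4.1 counts worsening of a condition the patient already has as an AE, and states: "The term AE is used to include both serious and non-serious AEs".
- Section 6.4.2 makes in-patient hospitalisation a seriousness criterion.
- Section 6.4.4: "All SAEs have to be reported, whether or not considered causally related to the investigational product".

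Sections 6.4.1, 6.4.2 and 6.4.4 do not mention a progression exception.

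**The concern.** Progression exemptions are a known way to keep expected worsening of the disease out of the AE listings. They normally stop where an event becomes serious or ends treatment, and this one does not. The disease under study is type 2 diabetes in patients already uncontrolled on two agents, so worsening glycaemia is the natural candidate for the label. The judgement is left to the investigators at about 30 centres, and the protocol gives no criterion for when attribution is unequivocal.

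What is at stake is the SAE report itself: the notice to the sponsor by the end of the next business day, the onward transmission to pharmacovigilance under 6.4.4, and the entry in the safety summaries of 12.2.2. The rule decides what a site enters in the eCRF, so a later analysis plan cannot restore an event that was never entered as an AE or SAE.

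**Working it through.** No calculation applies; the check is to run two cases through the rules.

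**Case 1: investigational product stopped for confirmed high FPG.**
- FPG is a protocol-mandated central-laboratory value at Visits 3 to 9 (Table 2).
- Section 5.8 lists confirmed high FPG as a study-specific discontinuation criterion in two visit windows, the later one being "FPG > 12.2 mmol/L (>220 mg/dL) during the double-blind treatment period, between Visit 6 and Visit 9".
- Under 6.4.3.6, first paragraph, the value is an AE because it is the reason for discontinuation.
- Under 6.4.3.6, third paragraph, the same value is not an AE if the site regards it as unequivocal progression.
- Neither paragraph says which prevails.

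**Case 2: unplanned hospital admission for worsening glycaemia.**
- The protocol foresees such admissions: section 5.8, criterion 1, distinguishes hospital stays whose primary reason is glycaemic control from those with another reason.
- Under 6.4.1 the worsening of a pre-existing condition is an AE. Under 6.4.2 the admission makes it an SAE. Under 6.4.4 it must be reported.
- Under 6.4.3.7 the event is not reported as an AE if judged unequivocal progression. Because 6.4.1 defines AE to include serious AEs, this removes the SAE as well.
- If the site treats the event as a laboratory deterioration, 6.4.3.6, third paragraph, reaches the same result and names SAE outright.

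**Does another rule catch Case 2?**
- The second paragraph of 6.4.3.6 has accompanying signs and symptoms reported as AEs, but 6.4.3.7 counts increased symptoms of the disease as progression.
- The list in 6.4.2 of events sent on SAE timelines whatever their seriousness covers pancreatitis, opportunistic infections and a liver-test combination. None is glycaemic.
- The medical review in 11.2.2 works from the AE list, so it cannot retrieve an event that was never recorded as an AE.

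In both cases the opposing rules apply to one event and give opposite instructions once the site attributes the event to progression.

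**The case against.** The strongest reply is that 6.4.3.6 is coherent as drafted: the first paragraph is a general filter and the third a narrow exception to it. That reading is fair and can settle Case 1 within the section, although precedence is not stated. It does not settle Case 2. It confirms that a hospitalisation judged to be progression goes unreported, against 6.4.4, which carries no such exception.

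The second reply is that the exemption is narrow. This stands. Only unequivocal progression is exempt, and neither section names hyperglycaemia. A high FPG may reflect poor compliance, glucocorticoids or lack of effect, and those cases stay reportable. A reader might infer that sites are told not to report hyperglycaemia in general; the text does not say so.

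Third, the glycaemic data are not lost. This also stands. FPG and HbA1c are measured centrally from Visit 3 to Visit 9 and the reason for stopping is still captured. What can be lost is the AE or SAE report.

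Fourth, Appendix B already excludes some admissions for pre-existing disease. That clause covers planned admissions where the disease has not worsened unexpectedly. It narrows the affected set, but does not reach an unplanned glycaemic admission.

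Three further readings are tempting and not supported:
- **That Appendix B assumes the opposite of 6.4.3.7.** Its sentence, "Causal relationship in cases where the disease under study has deteriorated due to lack of effect should be classified as no reasonable possibility", concerns lack of effect. Cases that are not unequivocal progression can be recorded and then rated under it, so the two can coexist.
- **That the under-reporting is unbalanced between arms.** More glycaemic deterioration on placebo would be plausible if saxagliptin works, but the protocol gives no rate of glycaemic discontinuation or hospitalisation by arm. Neither a size nor a direction can be stated.
- **That the protocol confuses glycaemic with AE discontinuations.** Section 5.8 lists safety reasons separately from the numbered FPG criteria. How to tabulate them is an analysis choice.

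**Conclusion.** The concern holds in a limited form. The exemption in 6.4.3.6 (third paragraph) and 6.4.3.7 has no exception for events that meet a seriousness criterion or end treatment. It conflicts with the first paragraph of 6.4.3.6 and with 6.4.1, 6.4.2 and 6.4.4. The conflict over serious events is the part that matters, and no reading of 6.4.3.6 alone removes it.

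The documents support no numerical size. For each affected event the result is one SAE report or none, according to the paragraph the site follows. This rests on one assumption: that some sites will judge a serious or treatment-ending glycaemic event to be unequivocal progression, which the protocol permits without giving a test. The primary HbA1c analysis and the sample size are not touched.

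**What to change.** Reconcile the passages by amendment:
- In 6.4.3.6 (third paragraph) and 6.4.3.7, state that the exemption does not apply to any event that meets a seriousness criterion in 6.4.2 or is the reason for discontinuing investigational product.
- Strike SAE from the AE/SAE wording of the exemption in 6.4.3.6.
- State that such events are always recorded, with causality rated as Appendix B describes.

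The exemption then still does its proper work for non-serious worsening that does not end treatment. The cost is a change of wording in two sections and a note in the eCRF completion instructions. Reported AE and SAE counts may rise slightly. No dose, stopping rule or other clinical management changes.
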